To ensure that this study has enough participants after accounting for a 20% inadequate visualization of the POCUS image, the investigators will need to recruit 1483 participants. The investigators target to complete the recruitment within 12 months.

Data collection

The investigators trained with POCUS will recruit and screen patients in the ED during the study period using an ultrasound device throughout the study and all images will be stored for regular review by an echocardiologist.

POCUS screening will be conducted to measure the maximum diameters at end diastole of the aortic root, ascending aorta, aortic arch, and descending thoracic aorta. The internal diameter will be measured perpendicular to the axis of blood flow and leading edge to leading edge in accordance with the guidelines set forth by the American College of Cardiology.(12) Measurements of the aortic root and ascending aorta will be taken using parasternal long-axis views, while the aortic arch will be assessed from the suprasternal view. The descending thoracic aorta will be examined using modified apical 2-chamber and subcostal views. The investigators will also specifically look for an intimal flap, pericardial effusion and aortic regurgitation.

The investigators will inform the emergency physicians under the following conditions:

- 1. patient has an aortic diameter \geq 5cm
- 2. patient has an intimal flap, pericardial effusion or moderate aortic regurgitation

If physicians identify a clinical possibility of TAA, these patients will be referred to cardiothoracic surgeons. If there is a suspicion of acute aortic syndrome, the ED physicians will consult cardiothoracic surgeon urgently \pm CTA in the ED as usual practice.

Relevant clinical data (such as past medical history, laboratory results, operation records etc.) will also be collected. In addition, the investigators will follow up with the patients for 28 days to monitor mortality and any advanced imaging performed outside the ED.

Outcome measurement

The primary outcome is the number of patients with TAA (a maximum aortic diameter of \geq 4.5 cm and/or \geq 50% localized enlarged diameter relative to the adjacent normal segment as indicated by POCUS).

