The secondary outcomes include the number of patients with confirmed TAA as verified by CTA, BMI for all participants, the number of CTA scans conducted for TAA confirmation, the number of surgical interventions performed among TAA patients, the ICU admission rate, ICU length of stay, hospital length of stay and mortality, proportion of adequate visualisation of POCUS studies obtained, agreement of aortic diameter measurement between CTA and POCUS, and signs and symptoms of TAA patients presenting to the ED. In addition, the investigators will assess the 28-day all-cause mortality and any advanced imaging done outside the ED for evaluating the aorta.

Statistical analysis

Patients with a maximum aortic diameter ≥ 4.5 cm and/or $\geq 50\%$ localized enlarged diameter relative to the adjacent normal segment are regarded as TAA while those with an aortic diameter < 4.5 cm are regarded as non-TAA. Comparison of baseline characteristics and aortic size measurements will be made between these two groups of patients. Categorical variables will be compared with Chi square test or Fisher's exact test. Continuous variables will be compared using Student's t-test or Mann-Whitney U test, based on the results of the Shapiro-Wilk W test. Binary logistic regression analysis will be used to identify the risk factors that associated with TAA independently and to predict the presence of TAA. Variables with a p < 0.2 from the univariate analysis will be included in the stepwise logistic regression model. In patients who underwent a CTA, the investigators will assess the agreement of aortic diameter measurements between CTA and POCUS using Bland-Altman analysis. All statistical analyses and visualisations will be done using R or Prism GraphPad.(13, 14) A significance level of 0.05 will be considered statistically significant.

Patients with missing data on certain variables will be removed from that particular analysis. POCUS studies with inadequate visualisation of all views will be discarded.

Ethics

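### A scan that shows only part of the aorta, with normal visible segments, is counted as non-TAA under the literal rule, which biases overall prevalence downward by an unknown amount

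*Protocol*

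**What the plan says.** All references are to the protocol; no SAP is at hand.

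- **Data collection** asks for maximum diameters of four segments: root, ascending aorta, arch and descending thoracic aorta. The root and ascending aorta are measured from the parasternal long-axis view and the arch from the suprasternal view only. For the last segment, "The descending thoracic aorta will be examined using modified apical 2-chamber and subcostal views".
- **Outcome measurement**: "The primary outcome is the number of patients with TAA", judged by a maximum diameter of at least 4.5 cm and/or a localised enlargement of at least 50% over the neighbouring normal segment. A secondary outcome is the "proportion of adequate visualisation of POCUS studies obtained".
- **Statistical analysis** defines the TAA group in the same way, "while those with an aortic diameter < 4.5 cm are regarded as non-TAA". Its closing lines set two rules: "Patients with missing data on certain variables will be removed from that particular analysis", and then "POCUS studies with inadequate visualisation of all views will be discarded".
- **Sample size calculation** raises the evaluable 1186 to 1483 after "accounting for a 20% inadequate visualization of the POCUS image".

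Nowhere does the protocol say which segments must be seen before a patient can be called non-TAA, or how a scan with some adequate and some inadequate views is classified.

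**The concern.** TAA status is decided by the largest of four measurements taken through different windows. Such a rule is asymmetric: a single qualifying segment proves TAA whatever else is hidden, while absence of TAA is established only if all segments were visible. The discard rule ignores this. It removes a study only when no view worked, so every other scan stays in and is classified on whatever was visible.

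For example, a patient with a 3.8 cm root and no usable arch or descending view has a largest observed diameter below 4.5 cm and joins the non-TAA group. The enlargement criterion has the same weakness, because it cannot be applied where the neighbouring segment is unseen.

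The Aim is the prevalence of TAA in hypertensive patients in the ED. If partly examined patients sit in the denominator as negatives, that prevalence is understated, and a reader cannot tell by how much because the protocol does not ask for adequacy by segment.

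**Working it through.** **1. The plan's own figures reproduce.** Inputs from Sample size calculation: AUC A = 0.857, prevalence p = 0.075, 95% confidence, margin 0.05. The Hanley-McNeil variance of an AUC is [A(1−A) + (n₁−1)(a−A²) + (n₂−1)(b−A²)] / (n₁n₂), with a = A/(2−A) = 0.7498 and b = 2A²/(1+A) = 0.7910. At N = 1186, n₁ = 88.95 and n₂ = 1097.05. This gives SE = 0.02550 and half-width 1.96 × 0.02550 = 0.04998, and 1186 is the smallest N that meets 0.05. The inflation is 1186/0.8 = 1482.5, rounded up to 1483. The arithmetic is not at fault.

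**2. Sampling error of the prevalence.** 1.96 × √(0.075 × 0.925/1186) = 0.0150, or about 1.5 percentage points, with 1186 × 0.075 ≈ 89 expected cases.

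**3. Direction of the bias.** Under the literal rule a visible qualifying segment still counts as TAA. The only possible error from an unseen segment is a missed aneurysm, so the effect on prevalence is zero or negative, never positive.

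**4. Size, by assumption only.** Let f be the share of retained scans that are partial (taken as equal in patients with and without TAA). Let m be the share of TAA patients with partial scans whose aneurysm lies only in unseen segments. Reported prevalence = p(1 − f·m). The protocol gives neither f nor m.

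| f | m | reported, if true value is 7.5% | cases missed of 89 |
|---|---|---|---|
| 0.1 | 0.1 | 7.42% | 0.9 |
| 0.2 | 0.25 | 7.12% | 4.4 |
| 0.4 | 0.25 | 6.75% | 8.9 |
| 0.6 | 0.5 | 5.25% | 26.7 |

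The shortfall runs from 0.08 to 2.25 points, that is, from negligible to more than the 1.5-point half-width.

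**5. A tempting repair that fails.** Suppose the denominator is all fully seen studies plus all positives, including positives from partial scans. With c the share of retained studies fully seen and every positive detected, the estimate is p/[c + p(1−c)]. For p = 7.5% this is 8.3% at c = 0.9, 9.2% at c = 0.8 and 13.7% at c = 0.512. It is biased upward because partial positives are kept while partial negatives are dropped. Nor is it an upper bound, which would require counting every indeterminate scan as positive.

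**The case against.** The strongest reply is that the preceding sentence already covers this: "Patients with missing data on certain variables will be removed from that particular analysis". Each segment diameter is a measured variable, so the two sentences could be read as a pair. A scan with no usable view is discarded, and a scan with some segments missing leaves the analyses that need them. That reading is possible. But the protocol never says that an unseen segment makes the maximum diameter missing, and if it did, a patient with a plainly visible aneurysm and one failed window could be removed too. The sentence adds an alternative without settling the question.

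Three further objections stand:

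- The size of the bias rests on assumed shares, and the milder cases fall well inside sampling error.
- The primary outcome is a count of patients positive on POCUS. Relabelling partial negatives does not alter that count; it alters the non-TAA group and the prevalence denominator.
- Detailed bounding analyses often belong in a SAP. Here, however, the protocol states both a discard rule and a non-TAA rule, and following them as written gives a biased prevalence.

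A reader might infer that the 20% allowance fits neither reading of the discard rule. If three window groups each failed independently in 20%, all would fail in 0.2³ = 0.8% (about 12 of 1483), and at least one would fail in 1 − 0.8³ = 48.8%, leaving about 759. But operator skill and body habitus would plausibly make failures occur together. With full correlation both readings discard 20% and leave 1483 × 0.8 ≈ 1186, as planned. The allowance is unspecified, not shown to be wrong.

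A reader might also infer that the BMI and risk-factor comparisons are distorted. That is plausible, but nothing in the protocol establishes its direction or size.

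**Conclusion.** The point holds as a fault in a stated rule. With the non-TAA rule and the discard rule taken literally, patients whose aorta was only partly seen count as negative, and overall TAA prevalence is biased downward. The direction rests only on the definition of TAA as a maximum over four segments and on the literal reading of the discard sentence. The size cannot be derived: 0.08 to 2.25 points on a true 7.5% is an illustration under assumed f and m, and the real effect may be small.

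The protocol's wording does not support a claim that visible aneurysms will be discarded. That would need the sentence to mean any inadequate view, which is not its natural sense. The sample-size arithmetic is sound.

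**What to change.** In Statistical analysis, replace the discard sentence with a rule by segment:

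1. Record for each of the four segments whether it was adequately seen.
2. Count TAA if any seen segment meets the definition, whatever else was unseen.
3. Call a patient non-TAA only if all four segments were seen and none qualifies. Label a partly seen scan with no qualifying segment indeterminate, keep it in the data set and report the number.
4. Report prevalence per segment over the patients in whom that segment was seen.
5. For overall prevalence report two figures: (i) all retained studies with indeterminates counted as negative, labelled a lower bound with respect to unseen segments; and (ii) prevalence among studies with all four segments seen, taking positives and negatives from that set only, as a sensitivity estimate. The second is free of bias only if visibility is unrelated to having TAA, which should be said. Do not use fully seen studies plus all positives.
6. State whether an unseen segment makes the maximum diameter missing under the missing-data sentence.
7. In Sample size calculation, state whether the 20% means no adequate view or any inadequate view.

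The cost is protocol wording and one adequacy tick per segment on the data form. The results will show an indeterminate group, and the fully seen estimate will be less precise. If, for illustration, 80% or 50% of 1186 studies were fully seen (949 or 593), its 95% half-width at 7.5% would be about 1.7 or 2.1 points instead of 1.5. No extra scans are needed for the lower bound or the per-segment figures.

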All participants will provide written informed consent. Patients' relatives can provide consent if the patient is not mentally capable of doing so. If no relatives are present in the ED, the investigators will obtain deferred consent as soon as the patient is awake. If the patient passes away before they can consent to this study, all images and data collected will be discarded. No images and data will be used without consent. Participants are allowed to withdraw from the study at any time during the study period and their data will be discarded. This study will be conducted in full compliance with the Declaration of Helsinki and the principles of Good Clinical Practice. The investigators will seek ethical approval from our local review committee.

Funding and Sponsor

There is no funding or sponsorship for this study.

Potential Conflicts of Interest

The PI and CI have declared no potential conflicts of interest.

Safety Management

Ultrasound is a safe screening tool and does not cause any adverse effects to patients. Any incidental findings of aortic abnormalities will be reported to the attending physician. The investigators will abort the POCUS scan immediately and inform the attending physician in the event of any deterioration. Necessary resuscitation will be initiated without further delay.

Cost and Benefit for Participants

There is no additional charge or reward for participation in this study.

Confidentiality and privacy

Ultrasound images will be stored in both the device and the CUHK internal drive. All clinical data will be collected using the CU WebForm and will be kept confidential. Data will be destroyed 7 years after the publication of the study. Signed consent forms will be saved in a locked cabinet in the research office.

References

4. Digital Policy Office. Inpatient Discharges and Deaths in All Hospitals Classified by Disease for the Year 2022 (English). https://data.gov.hk/en-data/dataset/hk-dh-dh_ncddhss-ncdd-dataset-102022.

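### Minor: the deferred-consent rule removes patients because they died, while mortality is a secondary outcome; a count of removals and a clear label would cover it

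*Protocol*

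**What the plan says.** The Ethics section opens with a general rule: "All participants will provide written informed consent". Two provisions cover patients who cannot consent for themselves. The first uses relatives: "Patients' relatives can provide consent if the patient is not mentally capable of doing so". The second applies when there are none: "If no relatives are present in the ED, the investigators will obtain deferred consent as soon as the patient is awake".

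Three provisions then remove data:

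- Death before consent: "If the patient passes away before they can consent to this study, all images and data collected will be discarded".
- No consent for any reason: "No images and data will be used without consent".
- Withdrawal: "Participants are allowed to withdraw from the study at any time during the study period and their data will be discarded".

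Mortality is an outcome in two places. Under Data collection, "the investigators will follow up with the patients for 28 days to monitor mortality". Under Outcome measurement, mortality stands in the list of secondary outcomes, and in addition "the investigators will assess the 28-day all-cause mortality".

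The exclusion criteria rule out trauma patients and patients in cardiopulmonary resuscitation. The protocol does not mention a count of patients removed under the Ethics rules. It does not forbid one either.

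**The concern.** Most consent rules restrict the study population without looking at the outcome. This one differs on a single route. A patient scanned under deferred consent stays in the data by surviving long enough to consent and agreeing, and drops out by dying first. For those patients the outcome being reported decides whether they are counted.

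What is at stake is how the mortality figure is read. Without a label, a reader would take it as the mortality of hypertensive ED patients who were scanned. In part it is the mortality of those who lived to give consent. The count is also a matter of timing: an analysis plan written later can choose how to present mortality, but it cannot recover a number that nobody recorded before the data were discarded.

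**Working it through.** **Inputs from the protocol.** Recruitment target 1483 (Sample size calculation). It reproduces from the protocol's own figures: 1186 / (1 − 0.20) = 1482.5, rounded up to 1483.

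**Inputs that are assumed.** The protocol gives no death rate, no share of deferred consent and no withdrawal rate. Take N = 1483 patients scanned, D = 15, 30 or 74 true deaths, and k = 1, 3 or 5 deaths before consent.

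**Effect of the rule alone.** True mortality is D/N. Observed mortality is (D − k)/(N − k), which is below D/N whenever k > 0 and D < N.

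| True deaths | True mortality | k = 1 | k = 3 | k = 5 |
|---|---|---|---|---|
| 15 | 1.01% | 14/1482 = 0.94% | 12/1480 = 0.81% | 10/1478 = 0.68% |
| 30 | 2.02% | 29/1482 = 1.96% | 27/1480 = 1.82% | 25/1478 = 1.69% |
| 74 | 4.99% | 73/1482 = 4.93% | 71/1480 = 4.80% | 69/1478 = 4.67% |

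Before rounding, the fall for one discarded death is 0.067, 0.066 and 0.064 percentage points. For scale, the 95% Wilson interval for 30/1483 is 1.42% to 2.87%, so even five discarded deaths (1.69%) stay inside it.

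**Choice of denominator.** The 1483 may be read as consented participants only, so that pre-consent deaths come on top. With 30 deaths among those scanned and k = 3, the comparison is then 30/1486 = 2.019% against 27/1483 = 1.821%, a fall of 0.198 points. The table's version gives 0.199 points. If mortality were computed on the 1186 with adequate images, one discarded death would cost slightly more: 24/1186 = 2.024% against 23/1185 = 1.941%, or 0.083 points.

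**Removals that act the other way.** Let w survivors be discarded because they withdraw or never consent. Setting (D − k)/(N − k − w) = D/N gives w = k(N/D − 1). To cancel one discarded death takes:

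- 15 deaths: 1483/15 − 1 = 97.9, about 98 survivors
- 30 deaths: 1483/30 − 1 = 48.4, about 48 survivors
- 74 deaths: 1483/74 − 1 = 19.0, about 19 survivors

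**28-day mortality.** A patient who dies unconsented after day 28 leaves only the denominator. With 30 deaths by day 28 the change is 30/1482 − 30/1483 = 0.0014 points upward, which is negligible.

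**What the sensitivity figure would show.** Take 30 true deaths, k = 3 and w = 15 other removals, all alive. Consented patients give 27/1465 = 1.84%. Adding the three deaths to numerator and denominator and the 15 to the denominator gives 30/1483 = 2.02%, the true value. Adding back the deaths alone gives 30/1468 = 2.04%, slightly too high, so the other removals belong in the denominator too.

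**The case against.** The strongest reply is that this is an openly stated ethics rule, not an analysis error. Every figure in the study describes consenting patients, the protocol never claims to estimate mortality in all scanned patients, and participant flow is commonly left to the analysis plan or the report. Much of this stands. The rule is legitimate, and an anonymous count needs no change to it. What does not follow is that the count can wait: it has to be kept while patients are being removed.

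The second reply is size. The affected group is narrow: no capacity, no relative present, not in resuscitation, not trauma, and dead before consenting. Mortality is in neither the aim nor any of the three objectives. The discard of scans with inadequate views may remove far more patients; the protocol allows 1483 − 1186 = 297 for it. This stands and keeps the point minor. It does not remove it, because loss through poor images is not defined by death.

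The third reply concerns the remedy. If the vital status of the other removals were shown as a full range, the example above would run from 30/1483 = 2.02% to 45/1483 = 3.03%. That is about 1.0 point wide, against a shortfall of 0.18 points (1.84% against 2.02%). Nearly all of that width would come from withdrawals and missing consents, not from the rule at issue. This is right, and one figure with a caveat serves better than a range.

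A reader might also infer that reported mortality will be too low overall. The documents do not support that: they give no rates, and discarded survivors push the figure up.

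**Conclusion.** The point holds as a minor, cheap improvement. On the deferred-consent route, inclusion depends on survival, so the rule by itself lowers observed mortality. The size is about 0.06 to 0.07 percentage points per discarded death, assuming about 1483 patients and 15 to 74 deaths. The direction of the rule alone follows from arithmetic; the size rests wholly on assumed rates. The net direction after all removals is not fixed.

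A reader might go further and conclude that the discard rule is wrong or that the study's main result is threatened. Neither is supported. Not using data without consent is a proper choice, the protocol does not forbid a count, and nothing in it suggests a material effect on the primary outcome.

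**What to change.** Keep the discard rule unchanged and add the following.

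1. Subject to ethics-committee agreement, keep from the start of recruitment an anonymous count of scanned patients who are removed, by reason only: died before consent, withdrew, consent not obtained for another reason. Show it in the flow diagram.
2. Label mortality and 28-day mortality as conditional on surviving to consent.
3. If the count is permitted, give one sensitivity figure that adds the pre-consent deaths to numerator and denominator and the other removals to the denominator, with a note that the vital status of the latter is unknown.
4. If the count is not permitted, use the label alone.

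The cost is one line in the screening log, the committee's agreement and one line in the report. The mortality figure may look slightly less favourable.
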